Activity	Screen	Pre-op (baseline)	Pre-op after epidural, before bolus	Pre-op after epidural, after bolus/before anesthesia	Intra-op	Post-op Recovery (PACU)	1 hour post-op	Transfer to floor	POD 1	POD 2	POD 3
Informed consent	Х										
Inclusion / Exclusion Criteria	Х										
Medical History	Х										
Randomization		Х									
IV Placement		Х									
Primary measurements(SBP,DBP,MAP, HR,SaO2,RR,Pain score?) every 3-5 min		х	х	х	х						
Epidural Placement		Х									
Administration of Pre-op sedation			х								
Prep and supply of test drug			Х								
Infusion of Study drug if randomized for test group				х							
Infusion of Ropivacaine				х							
Primary measurements every 15 min						х	х				
(Secondary measurements) Sensory block assessment (1 hour post-op and every 6 hours for the subsequent 72 hours						x	х		x	x	x
Intra-op surgical records					Х						
Anesthesia Pain Service records			х	х	х	х	х	х	х	х	х
Pain Scores DVPRS Score							Х		Х	Х	Х
Record 24 hour I/Os						Х			Х	Х	Х
Pain management and "Rescue Drug" administration as needed							х	х	х	х	х
Record opioid usage						Х	Х	Х	Х	Х	Х
All SOC points and monitors: EKG, non-invasive BP; ETCO2; pulse ox; arterial line with Flow Track (if indicated); peripheral or central venous line; induction and mode of anesthesia.		x									
Physical therapy rehabilitation records (Time and distance of ambulation)									x	х	х

Patients will be approached about their willingness to participate in this study either in a pre-operative surgical or anesthetic clinic visit or in the pre-operative area on the day of surgery. Consent will be obtained by a member of the research team. The patient will be given time to read the consent, have all study related questions answered, and discuss the study with their family, if desired. A copy of the signed consent will be placed in the patient's physical chart, and a research progress note documenting study enrollment will be made in the patient's electronic medical record.

Inclusion criteria:

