Up to 250 patients between the ages of 18 and 80 years undergoing epidural analgesia to treat perioperative pain associated with major surgery will be approached for their willingness to participate in the study. Patients undergoing major thoracic, abdominal, urological or orthopaedic surgery for whom thoracic or lumbar epidural block would be indicated and planned for intraoperative and postoperative analgesia as per the UF Acute Pain Service (APS) usual and routine practice will be included in this study. Our epidural failure rate is lower than 20% and our institution performs around 100 epidurals a month. If only a 1/3 of our patients agree to be part of our study we would have 24 study patients a month. This would then mean that our study would take 10 months to complete data collection.

Exclusion criteria:

Sepsis (febrile, above normal and upward trending white blood count, and/or positive cultures for systemic infection), patients with acute trauma, coagulopathy [INR >1.4, platelets < 100,000, and/or anticoagulation medication given out of UF APS adaptation of the American Society of Regional Anesthesiologists (ASRA) guidelines⁹, preoperative hemodynamic instability, symptomatic coronary artery disease (angina etc.), patients from the ICU whose tracheas were intubated for any cause, patient refusal, pregnancy, allergies to medications in the protocol, and primary or secondary block failure.

Standard of Care - Preoperative Period:

All patients will receive a standardized continuous epidural block at the appropriate level for the planned surgery by the APS physician staffing the block room that day. For the standardized continuous epidural block, placement will be confirmed with loss of resistance technique (LORA), wave form analysis or nerve stimulation.

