Patients will receive a bolus of 500 mL of 5% Albumin intravenous infusion as per the usual routine practice of the APS before the main bolus dose is injected. A preoperative level of block will be established that is appropriate for the surgery by injecting an appropriate volume of ropivacaine 0.5% or lidocaine 2% w/ epinephrine 1:200,000 (5–10 mL) into the epidural space as per the usual practice of the APS. This will be done after the routine test dosing with 3 mL of 2% lidocaine and 1:200,000 epinephrine, confirmed that intrathecal and intravascular markers are negative. If an insensate-to-cold area in the appropriate dermatomes cannot be established within 10 minutes following a 5 to 10 mL (maximum 10 mL) injection of ropivacaine 0.5%, the epidural catheter will be removed and replaced. If this process is repeated and there was still no level, it will be annotated and the patient will be removed from the study, labeled as a primary block failure, and treated appropriately by the attending anesthesiologist by either repeating the epidural block placement a third time or using other appropriate perioperative analgesia.

Research-Related Procedures - Preoperative Period:

Once consent is obtained, patients will be randomly allocated by computergenerated randomization to one of four groups. This will be a quintuple blinded prospective study. The anesthesiologist managing the intraoperative anesthesia, the anesthesiologists (APS) placing the blocks and following the patients on the floors, the research nurse taking the measurement, the surgeons, nor the patients will be aware of what combination of drugs are used for the epidural block infusion.

The three groups will consist of:

- 1. Group A (Ropivacaine 0.2% infusion; Control group)
- 2. Group B (Ropivacaine 0.2% + 2 mcg/mL epinephrine)

3. Group C (Ropivacaine 0.2% + 5 mcg/mL epinephrine)

The pharmacists will make up and supply test drugs for groups A, B and C and provide them labeled to the block area drug dispenser as "A, B, or C test solutions" without specifically identifying the content.

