Immediately following the establishment of an appropriate level for the planned surgery, an infusion of the test drug will be initiated at 4 to 8 mL per hour with a 4- to 8-mL patient-initiated bolus at a lockout interval of 1 hour – typically 8 mL per hour for major abdominal or thoracic surgery and thoracic epidural placement and 4 mL per hour for hip arthroplasty and lumbar epidural. Once established as effective for the clinical situation, this infusion will be left unchanged throughout the surgery and postoperative period. If clinically indicated, and the infusion rate is changed to below the limits of 4 – 8 mL per hour, this indicates the end of the need for the epidural infusion or otherwise untreatable hypotension.

Standard of Care - Intraoperative and Postoperative Periods:

Intraoperative and postoperative fluid management will be at the discretion of the anesthesia and primary teams.

Preoperative sedation will be a maximum of 5 mg of midazolam by intravenous injection (IV) and alfentanil 2000 mcg IV. Monitors include: EKG, non-invasive blood pressure, ETCO2, pulse oximeter, arterial line with Flow-Track (if indicated and appropriate per intra- or postoperative operative anesthesiologist), peripheral intravenous or central venous line as deemed appropriate by the attending intra- or postoperative operative anesthesia and mode of anesthesia (maintenance, fluid management, intraoperative analgesia, muscle relaxation, etc., are at the discretion of the attending intraoperative anesthesiologists.

If hypotension (see definition below) is encountered intraoperatively, the attending anesthesiologist will start a vasoactive or positive inotropic medication as indicated by the patient's medical requirements.

Research-Related Procedures – Intraoperative:

- Anesthesiologists will be encouraged to use alpha agonists if the other causes of hypotension are excluded and lumbar epidural is judged to be a contributory cause of the hypotension; and epinephrine, dobutamine, or dopamine (or indirect inotropic agents such as ephedrine) if thoracic epidural is judged to be the cause of the hypotension and the other causes of hypotension such as hypovolemia have been ruled out.

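### Randomisation comes before the block is shown to work, so primary block failures are allocated and then removed without study drug, with no loss allowance or analysis set in the plan

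*Combined protocol and SAP*

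**What the plan says.** **Allocation.** Research-Related Procedures - Preoperative Period: "Once consent is obtained, patients will be randomly allocated by computergenerated randomization to one of four groups". The schedule table in section 6 agrees. It marks randomisation in the pre-operative baseline column, before the columns for the period around the bolus.

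**Start of study drug.** The same section: "Immediately following the establishment of an appropriate level for the planned surgery, an infusion of the test drug will be initiated".

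**Removal in between.** Standard of Care - Preoperative Period describes a first placement, a replacement if no level is found, and then: "If this process is repeated and there was still no level, it will be annotated and the patient will be removed from the study". These patients are classed as primary block failures.

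**Eligibility.** The exclusion criteria end with "allergies to medications in the protocol, and primary or secondary block failure". The schedule has inclusion and exclusion criteria checked at the screening visit, when neither kind of failure can be known.

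**Failure rate.** Inclusion criteria: "Our epidural failure rate is lower than 20" per cent. This is an overall figure, not split between failure before and after the infusion starts.

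**Numbers.** Sample size determination gives 200, as 50 per group, and mentions no losses. The figure of up to 250 under Inclusion criteria is the number of patients to be approached. The Data analysis plan names models but defines no analysis population.

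**Supply.** Pharmacists prepare three solutions and "provide them labeled to the block area drug dispenser as" solutions A, B or C. In the schedule, the row "Prep and supply of test drug" is marked after epidural placement but before the bolus.

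**The concern.** A criterion that can be assessed only after catheter placement and the loading bolus is applied to patients who have already been randomised. Some patients will therefore hold an allocation, receive no study drug and leave the study. The plan does not say whether they count towards the 200, whether they are replaced, or whether they are analysed.

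Three things are at stake:

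- **Power.** If 200 is the number randomised, every primary failure comes off a sample sized with no margin.
- **Arm balance.** The number left in each arm depends on where the failures happen to fall.
- **Concealment.** Each letter stands for the same solution in every patient. If the block team knew a patient's letter and had worked out its content, the decision to declare failure could be influenced.

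**Working it through.** **1. Sequence**

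| Step | Where stated | Order |
|---|---|---|
| Consent and eligibility check | Schedule, screening column | 1 |
| Randomisation | Schedule, baseline column; Research-Related Procedures - Preoperative Period | 2 |
| Epidural placement | Schedule, baseline column | 3 |
| Preparation and supply of test drug | Schedule, column after epidural and before bolus | 4 |
| Bolus, level check, replacement, removal if no level | Standard of Care - Preoperative Period | 5 |
| Study infusion | Research-Related Procedures - Preoperative Period | 6 |

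Step 5 removes patients after step 2 and before step 6.

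**2. Reproducing the plan's figures**

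Inputs from Sample size determination: N = 200, 50 per group (hence k = 4 groups), alpha 0.05, 80% power, f = 0.24, and a 26-point difference in incidence.

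- Group means: one-way ANOVA with noncentral F, df1 = k − 1 = 3, df2 = N − k = 196, λ = f²N = 0.0576 × 200 = 11.52. Power at f = 0.24 is 81.5%. The f detectable at 80% power is 0.236, which rounds to the stated 0.24.
- Incidence: the plan gives no base rate. Assuming 20% against 46%, with 50 per group and two-sided 0.05, power is 79.9%. The 26 points therefore reproduce at that base rate.

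The plan's figures hold for 200 patients analysed, in four groups, with no loss.

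**3. Loss before study drug, if 200 are randomised**

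The loss d is an assumption, since the documents do not give it; 20% is the ceiling. Patients left = 200(1 − d), λ = 0.0576 × patients left, and number needed to keep 200 = 200/(1 − d), rounded up.

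| Assumed loss | Left | λ | Power at f = 0.24 | Detectable f at 80% | Randomise to keep 200 |
|---|---|---|---|---|---|
| 0% | 200 | 11.52 | 81.5% | 0.236 | 200 |
| 5% | 190 | 10.94 | 79.2% | 0.242 | 211 |
| 10% | 180 | 10.37 | 76.7% | 0.249 | 223 |
| 15% | 170 | 9.79 | 74.0% | 0.256 | 236 |
| 20% | 160 | 9.22 | 71.1% | 0.264 | 250 |

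At the 20% ceiling (40 per group), power for 20% against 46% falls from 79.9% to 70.3%.

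**4. How far below the ceiling the loss may be**

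Removal before study drug needs two failed attempts. As an illustration only, if 20% were an independent rate per attempt, two failures in a row would have probability 0.20 × 0.20 = 4%, or 8 of 200.

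**5. If 250 were randomised**

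250 × (1 − 0.20) = 200, so even the ceiling would be covered. The protocol does not say this. The accrual estimate does not settle it either: 24 a month for 10 months is 240.

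**6. Number of groups**

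The protocol speaks of four groups but lists three, which is a separate point. If 200 were spread over three groups, power at f = 0.24 would be 86.4% with no loss and 77.3% with 160 left. The direction is the same.

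**The case against.** **A reader might infer that a fifth of patients, or 50 of 250, will be lost before study drug.** The documents do not support this. The 20% is an upper limit on all epidural failures. Some of those are found after the infusion has started and are removed under Research-Related Procedures – Intraoperative, and removal before study drug needs two failed placements. The 250 are patients approached, not patients randomised. The loss is unknown and may be small.

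**A reader might infer that these removals break the randomised comparison, or that the block team knows the letter when it declares failure.** Neither is shown. Primary failure precedes the study infusion, so the infusion cannot cause it. The protocol says that those placing the blocks do not know the drug combination and that labels do not identify the content. Failure follows a set cold-testing rule, applied twice. Under that blinding, the removals should not differ by arm.

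What remains is conditional. The documents do not say who holds a patient's letter or when it becomes visible, and the schedule puts drug supply before the bolus. Section 7 also has the pharmacy disclose a patient's epinephrine dose when side effects are suspected. With fixed letters, one disclosure could decode that letter for later patients. Bias would need the letter to be known, its content guessed and the failure call altered. The documents neither state this nor rule it out.

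**A simpler remedy exists:** keep the present order, define the analysis set and add a loss allowance. That would cover power and reporting. It would leave the exclusion criterion impossible to apply before randomisation and the concealment question open.

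**Conclusion.** The point holds as a low-cost improvement. Allocation precedes proof of a working block, primary failures are removed after randomisation without study drug, and the plan has neither a loss allowance nor an analysis set to deal with them.

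The size depends on an unstated loss. Power at f = 0.24 goes from 81.5% with none to 71.1% at the 20% ceiling, and a 5% loss already puts it below the planned 80%. This assumes 200 randomised to four equal groups; if 250 are randomised, the loss is covered. The expected harm is fewer patients and uneven arms. Bias at this step is a conditional risk only.

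The later removals, for inadequate block or hypotension once the infusion is running, carry the greater risk of bias because they follow exposure. Moving randomisation does not prevent them.

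**What to change.** 1. In the schedule table and in Research-Related Procedures - Preoperative Period, move randomisation to after an adequate level is confirmed, just before the test solution is taken from the block-area dispenser.
2. List primary block failure as a pre-randomisation screen failure. Secondary failure, which can be known only later, should not be written as an eligibility criterion.
3. Define the primary analysis set as all randomised patients. This keeps in those removed after exposure, provided that their measurements continue to be collected.
4. State in Sample size determination that 200 is the number randomised, and keep it distinct from the 250 approached.

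With steps 1 and 2, primary failures after randomisation fall to zero. Power at f = 0.24 stays at 81.5% as far as this source of loss is concerned, and the concealment question at this step disappears. The fixed letters remain a weakness later in the study.

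The cost is a small workflow change and a minor amendment. Allocation and the drug-supply step move to after the level check, and since the infusion is to start at once, the allocation must be ready to draw in the block area. The labelled solutions are already supplied there.

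### Study solutions carry the same letters whose contents the protocol prints, one letter per arm and with no stated key, so the written procedure does not secure the claimed quintuple blinding

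*Combined protocol and SAP*

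**What the plan says.** All of the key text stands in Section 6, Research-Related Procedures – Preoperative Period. The blinding claim is: "This will be a quintuple blinded prospective study". Five parties are named: the intraoperative anesthesiologist, the Acute Pain Service (APS) anesthesiologists who place the blocks and follow patients on the floors, the research nurse, the surgeons and the patients. The list ends "nor the patients will be aware of what combination of drugs are used for the epidural block infusion".

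The group list then gives the contents by letter. A is ropivacaine 0.2% as control, B adds 2 mcg/mL epinephrine, and the last entry is "Group C (Ropivacaine 0.2% + 5 mcg/mL epinephrine". Directly after this, the pharmacists are to "supply test drugs for groups A, B and C and provide them labeled to the block area drug dispenser as" test solution A, B or C, "without specifically identifying the content".

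Three other places bear on the point:

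- Section 7 (Possible Discomforts and Risks) has the pharmacy contacted for the epinephrine dose when unwanted effects could be due to it.
- The schedule of activities in Section 6 puts "Prep and supply of test drug" one column after randomization. It also lists "Infusion of Study drug if randomized for test group" on a separate row from the ropivacaine infusion.
- The Inclusion criteria text gives the expected accrual: "we would have 24 study patients a month".

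No section describes a scrambled letter-to-content code, a patient-specific container number, or who holds a key.

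**The concern.** The label is meant to hide the contents, but it shows the letter under which the protocol publishes them. The solutions go to the block area, where the blinded APS physicians work.

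Knowledge of the arm could affect decisions that feed the outcomes. Under Standard of Care – Intraoperative and Postoperative Periods, fluids are left to the clinical teams' discretion and the attending anesthesiologist starts a vasoactive or inotropic drug for hypotension. Under Research-Related Procedures – Intraoperative, the APS physician gives a further epidural bolus when coverage is inadequate and then judges between replacing the epidural and starting rescue medication. Average blood pressure, pain scores and opioid use all lie downstream of these choices. The Abstract adds that routine use of 5 mcg/mL epinephrine already varies with the APS physician's preference. That shows that opinions differ, but not which way a bias would run.

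**Working it through.** The plan states no figure for this point. The check is a comparison of texts, followed by a count of patients who share a label.

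**Step 1: label against group list.** The list defines A, B and C by content. The labelling sentence supplies drugs for groups A, B and C under the letters A, B and C. Nothing separates the two uses, so on a plain reading the label letter is the group letter. With the protocol and the label in hand, no code break is needed.

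**Step 2: is a key stated elsewhere?** No. Two phrases suggest that one was intended: the labelling sentence withholds the content, and Section 7 sends clinicians to the pharmacy for the dose. Neither says that the label letters differ from the printed ones.

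**Step 3: suppose a private key exists.** There is still one letter per arm. Disclosure for one patient gives the person informed the content of that letter, and so the arm of every other patient they know to carry it. If the letter is control, the other two letters are shown to contain epinephrine. Disclosure of two different letters to the same person reveals all three arms.

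**Step 4: how many patients share a letter.** Inputs are the stated 24 a month (which the plan makes conditional on a third of patients agreeing), three listed groups, and an assumed even split. As a rough check on the 24, the plan's inputs give 100 × 0.80 × 1/3 = 26.7. I keep the stated 24; using 26.7 would give 8.9 per letter and change nothing of substance.

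- New patients per letter per month: 24 / 3 = 8. With four groups, which the randomization sentence says, 24 / 4 = 6.
- Patients on the other two letters: 24 − 8 = 16 a month.
- Upper limit over the trial at the stated 50 per group: 50 − 1 = 49 other patients on the disclosed letter.
- Accrual per day: 24 / 30 = 0.8. The number on infusion at one time is 0.8 × duration. No duration is stated; for an assumed 2 to 5 days this gives 1.6 to 4.0 in all, and one third of that, 0.5 to 1.3, on the same letter. Exposure therefore falls mainly on later patients.

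**Step 5: what each labelling scheme leaves.** With k pharmacy-held codes per arm, 8 / k new patients a month share a code.

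| Scheme | New patients a month sharing a code |
|---|---|
| One secret letter per arm | 8 |
| Two codes per arm | 4 |
| Four codes per arm | 2 |
| Patient number | 0 other patients |

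These figures count shared labels. They do not measure bias.

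**The case against.** The best defence is that a key was intended. The pharmacy call in Section 7 would be pointless if staff could read the dose from the letter, and the labelling sentence plainly means to mask. On that view one clarifying sentence would suffice. This stands in part: it makes the literal reading uncertain and lowers the severity. It does not supply the missing statement, and it leaves the one-letter-per-arm weakness in Step 3.

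A reader might infer that blinding failed, or that all 24 patients a month were readable to staff. The documents do not support that. They describe a procedure, not its conduct, and they give no rate of code breaks. A disclosure also reaches only the person informed, and only for patients whose letter that person knows.

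A reader might also take the schedule row on infusing study drug to mean that whoever starts the infusion must know the arm. That is probably loose wording. Section 6 elsewhere has test drugs made for all three groups, control included, and starts a test-drug infusion without excepting control.

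Two limits on the routes of bias are fair. For hypotension the text calls for a drug according to medical need and steers the choice of agent by epidural site, so freedom is narrower than for fluids. And removal from the study is written without a named decision-maker; the one role named in the rule for turning the epidural down or off, the intensive care physician, is not among the five blinded parties. Removal therefore cannot be assigned to blinded staff. A first hypotension event that meets the numeric threshold is also less exposed than average pressure, pain or opioid use, because it precedes its own treatment.

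**Conclusion.** The point holds as a gap in the written procedure: the labels reuse letters whose contents the protocol prints, no key is stated, and each letter serves a whole arm. The text therefore does not secure the blinding it claims. This rests on the wording alone and is firm. The consequences are not: the size and direction of any bias are unknown. What can be sized is the sharing of labels, 8 new patients a month per letter, given the stated accrual and an even three-way split. Should-fix. A stronger grade is not warranted, because a pharmacy key may have been intended and no unblinding is shown.

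**What to change.** In Section 6, Research-Related Procedures – Preoperative Period, replace the letter labels with the patient's unique study number on every container, including resupply, and no group letter. State that only the pharmacy holds the list linking number to content. State that code breaks are made and logged one patient at a time, and keep the emergency access in Section 7 as it is.

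If same-day labelling is not workable, use several codes per arm, unrelated to the printed group letters and held by the pharmacy. Scrambling the letters without adding codes stops decoding from the protocol, but leaves the sharing in Step 5 as it was.

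The cost is pharmacy labelling and patient-linked resupply, in place of shared stock in the dispenser, for about 24 patients a month (0.8 a day). The schedule places drug supply after randomization, so the number exists when the container is labelled. The real constraint is time: for patients who consent on the day of surgery, the window between randomization and the start of infusion is short. No extra patients are needed, and no dose or clinical rule changes. Merging the two infusion rows in the schedule into one row for the assigned study solution is optional tidying.
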